3.1.1 Switching Treatment Pathways

Subjects who develop safety or tolerability concerns while on daily treatment with AR101 in any Treatment Pathway will have their dosing regimen adjusted per Section 6.8. It is possible that a subject who tolerated a nondaily regimen in the parent study will enter ARC008 on Treatment Pathway 1 but subsequently develop safety or tolerability concerns during Extended Maintenance. Such subjects, per investigator judgment, will switch from Treatment Pathway 1 to Treatment Pathway 2 to undergo Repeat Up-Dosing and continue maintenance dosing at 300 mg daily; alternatively, they can be discontinued from the study. Other situations may arise where the investigator decides that it is in the best interest of the

[figure not shown]
subject to switch to Treatment Pathway 2. All such cases must be discussed with the medical monitor who must agree prior to switching. The most likely scenarios are as follows:

- Simple nonadherence: Subjects who miss more than 2 consecutive scheduled nondaily doses (eg, QOD dosing regimen, subject misses Monday and Wednesday doses) during any part of the study other than for treatment of an AE or a dispensing error
- Medically necessary dose interruptions: Subjects who miss more than 4 consecutive scheduled nondaily doses due to medically indicated circumstances (eg, as part of the treatment for intercurrent AEs)
- Safety / tolerability concerns: Any subject on nondaily dosing having 1 related serious adverse event (SAE), 1 related AE graded severe, 2 related AEs occurring on separate occasions, both graded moderate, or 3 consecutive doses judged "not tolerated," will be transferred from Treatment Pathway 1 to Treatment Pathway 2 for safety reasons. Alternatively, they may be discontinued from ARC008.

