3.2 Study Visits and Periods

The study schematic is shown in Figure 1 and the study visits and periods are briefly described in the sections that follow. The details of procedures to be performed at each visit are provided in Section 7 and the Schedules of Events in the appendices.

Figure 1: Study Schematic

DBPCFC, double-blind, placebo-controlled food challenge; OLFC, open-label food challenge.

For subjects in Treatment Pathway 1, 2, or 4, initiation of AR101 in ARC008 occurs on the same day as or within 3 days after the Exit/Early Discontinuation visit in the parent study, unless specified otherwise in the parent study protocol. For subjects in Treatment Pathway 3 or 5, initiation of AR101 in ARC008 occurs on the same day as or within 10 days after the Screening/Baseline visit.

Treatment Pathway 2 only: Subjects who enter Treatment Pathway 2 in ARC008 soon after completing the ARC004 Early Discontinuation visit will enter the Repeat Up-Dosing Period after the Screening/Baseline visit. Subjects who complete the Repeat Up-Dosing Period or who tolerate AR101 300 mg/day for 2 weeks in ARC004 will proceed to the Initial Maintenance Period after the ARC008 Screening/Baseline visit. Subjects who complete both the Repeat Up-Dosing and Initial Maintenance Periods or receive AR101 300 mg/day for at least 24 weeks in ARC004 will proceed to the Extended Maintenance Period after the ARC008 Screening/Baseline visit.

In the event of a pandemic (eg, Coronavirus Disease 2019 [COVID-19] pandemic), epidemic, or other emergency not related to the study (eg, natural disaster, act of war or terrorism), restrictions may be issued at the country, state, regional, and/or local level that

may affect study conduct, the scientific integrity of the study, or the safety and well-being of study participants and study site staff. When such restrictions and associated challenges (eg, site closures; travel restrictions; quarantines; pandemic- or epidemic-related illness in subjects, parents, caregivers, or study site personnel) prevent the conduct of study site visits (ie, onsite) or access to study product for an extended period, changes to certain study procedures will be implemented in accordance with regulatory requirements to ensure subject safety and continued treatment, care, and sponsor oversight as described in Appendix 12.

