7.2.3 Initial Maintenance Period (Visits Every 8 Weeks for 24 Weeks)

Subjects who did not complete their AR101 maintenance regimen in an eligible parent study will have a Screening/Baseline visit and begin the Initial Maintenance Period in ARC008.

In the Initial Maintenance Period, clinic visits will occur every 8 weeks ± 1 week for 24 weeks (with the first visit designated as Week 8).

Subjects should withhold their daily home AR101 dose on in-clinic dosing days but should take all other prescribed medications as scheduled.

The guidelines for dose escalation and reduction are the same as during the Up-Dosing Period (Section 7.2.2).

7.2.3.1 Week 8 and Week 16

The following procedures will be performed before administration of the in-clinic dose of AR101:

- Monitoring and recording of AEs, including allergic symptoms
- Concomitant medication review
- Food allergen exposure update
- Return of unused AR101
- AR101 dosing compliance check
- Abbreviated physical examination
- Vital signs
- Urine pregnancy test, for sexually active females of childbearing potential only, at Week 8 only
- Completion of questionnaires:
 - ACT/C-ACT (for subjects with known asthma only) (before PEF assessment)
 - TNSS (for subjects with known allergic rhinitis only)
- PEF (should be measured at approximately the same time of day at each visit assessment)

After completion of these procedures, AR101 will be administered in the clinic as instructed in Section 5.2. Subjects will be monitored as instructed in Section 5.3.4.

The following procedures will be performed before discharge from the clinic:

- Monitoring and recording of AEs, including allergic symptoms
- Peanut allergy training

- AR101 dispensing
- Home dosing instruction (Section 5.2)

7.2.3.2 Week 24

The following procedures will be performed before administration of the in-clinic dose of AR101:

- Monitoring and recording of AEs, including allergic symptoms
- Concomitant medication review
- Food allergen exposure update
- Return of unused AR101
- AR101 dosing compliance check
- Complete physical examination
- Vital signs
- PEF (should be measured at approximately the same time of day at each visit assessment)
- Blood sample collection:
 - CBC
 - Immunology assessments
- Urine pregnancy test (for sexually active females of childbearing potential only)
- Completion of questionnaires:
 - ACT/C-ACT (for subjects with known asthma only) (before PEF assessment)
 - TNSS (for subjects with known allergic rhinitis only)

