9.1 Sample Size

There is no sample size calculation for this study. The sample size will be determined by the number of eligible subjects from each of the prior AR101 studies who participate in this study.

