7.4. DATA DERIVATIONS AND DEFINITIONS

The following definitions and derivations will be used throughout this study:

- Study Day is calculated as (assessment date date of first dose of AR101 in ARC008 + 1) for assessments and visits performed on or after the date of first dose of AR101 in ARC008, and (assessment date – date of first dose of AR101 in ARC008) for assessments and visits prior to the date of first dose of AR101 in ARC008. There will therefore be no Study Day 0.
- Baseline is defined as the last non-missing value prior to the first dose of AR101 in ARC008.
- Change from baseline is calculated as observed value after the first dose of AR101 in ARC008 baseline value.
- A duration expressed in months will be calculated by dividing the duration in days by (365.25 / 12).

• A duration expressed in years will be calculated by dividing the duration in days by 365.25.

The study periods are defined in Table 4 (used to create the study period flags) with the first and last dose dates for each study period being identified as follows:

Study Period	Treatment Pathways	First Dose Date	Last Dose Date
Initial Escalation	3 and 5	Date and time of first in-clinic dose at Initial Escalation Day 1	Date of latest in-clinic dose at Initial Escalation Day 1 or Day 2. Set the time to be 23:59 and 59 seconds on each of these respective days.
Up-Dosing	2	For subjects that do not undergo Repeat Up-Dosing: the date and time of first in-clinic or at home dose of treatment in ARC008 if prior to date of first Initial Maintenance Visit. For subjects that undergo Repeat Up- Dosing: the date repeat up-dosing (Treatment Pathway 2) was started.	Date of first in-clinic dose of 300 mg during the Up-Dosing period. For subjects who do not reach the 300 mg dose: the latest of the last in-clinic dose during the Up-Dosing period or the date of last dose at home. Set the time to be 23:59 and 59 seconds on the respective day.
	3 and 5	The day following the date of last in- clinic dose at Initial Escalation Day 2	Date of first in-clinic dose of 300 mg during the Up-Dosing period. For subjects who do not reach the 300 mg dose: the latest of the last in-clinic dose during the Up-Dosing period or the date of last dose at home. Set the time to be 23:59 and 59 seconds on the respective day.
Initial and Extended	1 and 4	Date and time of first in-clinic or at home dose of treatment in ARC008	Date of last dose of study product

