Maintenance	2, 3, and 5	The day following the date of first in- clinic dose of 300 mg during the Up- Dosing period. For subjects who did not enter the Up-Dosing period: the date of first Initial Maintenance Visit.	Date of last dose of study product
Follow-Up Observation	All (1-5)	The day following the date of last dose of study product	Date of Study Exit visit. For subjects without a date of Study Exit visit: the date of study completion.
Overall	All (1-5)	Date and time of first in-clinic or at home dose of treatment in ARC008	Date of Study Exit visit. For subjects without a date of Study Exit visit: the date of study completion.

Table 4Study Period Definitions

- The active treatment period is defined as the time period beginning with the date and time of the first dose of study product and ending with the date and time of the last dose of study product.
- Duration of active treatment period (days) for AR101 is calculated as the date of last dose minus the date of first dose of AR101 plus 1.

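### SAP Table 4 misassigns study periods for subjects who switch from Pathway 1 to Pathway 2 and for Pathway 2 subjects who enter directly at maintenance

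*SAP*

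**What the plan says.** SAP Section 7.4, Table 4 defines the study periods and the flags built from them. For Pathway 2 it gives two Up-Dosing starts. With Repeat Up-Dosing, the start is "the date repeat up-dosing (Treatment Pathway 2) was started". Without it, the start is "the date and time of first in-clinic or at home dose of treatment in ARC008 if prior to date of first Initial Maintenance Visit". Up-Dosing ends on the "Date of first in-clinic dose of 300 mg during the Up-Dosing period", or at the last dose if 300 mg is not reached. Maintenance for Pathways 2, 3 and 5 starts the next day, with one fallback: "For subjects who did not enter the Up-Dosing period: the date of first Initial Maintenance Visit". For Pathways 1 and 4, Maintenance runs from first ARC008 dose to last dose. Initial Escalation exists only for Pathways 3 and 5. The Overall row starts at first ARC008 dose for everyone.

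The Protocol allows three routes that these rules must handle:

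- **Switching.** Under Section 3.1.1, a nondaily Pathway 1 subject who meets any of several reaction criteria "will be transferred from Treatment Pathway 1 to Treatment Pathway 2 for safety reasons", or may be discontinued. Section 7.2.1 sends switchers directly to Repeat Up-Dosing without a new Screening/Baseline visit.
- **Direct entry to Initial Maintenance.** Visits in Section 7.2.3 are every 8 weeks ± 1 week, "with the first visit designated as Week 8".
- **Direct entry to Extended Maintenance.** Under Section 3.2, some subjects from ARC004 "will proceed to the Extended Maintenance Period after the ARC008 Screening/Baseline visit".

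SAP Sections 9.1, 9.2.1, 9.2.3, 9.11 and 9.12 tabulate TEAEs, anaphylaxis, food allergy episodes, exposure and rescue medication by study period.

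**The concern.** Table 4 is written as if repeat up-dosing were the first thing a Pathway 2 subject does in ARC008. For a switcher it is not: nondaily Extended Maintenance came first. That earlier time can include the related SAE, related severe event, repeated moderate events or non-tolerated doses that led to the switch. Safety is the primary objective, and the period tables are where a reader looks for the reaction profile of maintenance as distinct from up-dosing. Under the Pathway 2 rows these reactions would be missing from the Maintenance column. The direct-maintenance routes have a related fault: their rules depend on a visit that comes weeks after the first dose, or that never takes place.

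**Working it through.** There is no power or event figure to reproduce; the Protocol states that "There is no sample size calculation for this study". The check is to apply Table 4 literally to each route. Day 1 is first ARC008 dose. Two inputs are assumed for illustration: 1096 days of treatment in ARC008, and a switch after 90, 183, 365 or 730 days.

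**1. Switchers, Pathway 2 rows.** Protocol Section 3.2.3.1 restarts at 80, 120 or 160 mg and steps every 2 weeks through 120, 160, 200, 240 and 300 mg as applicable. With no delays, the first 300 mg dose falls 5, 4 or 3 steps later:

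- Up-Dosing days = 14 × steps + 1 = 71, 57 or 43.
- Maintenance days = 1096 − pre-switch days − Up-Dosing days. For a switch after 365 days and restart at 80 mg: 1096 − 365 − 71 = 660.
- Days in no component period = 1096 − 71 − 660 = 365, which is the whole pre-switch interval. The same holds for the other assumed switch times (90, 183 and 730 days).

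A switcher who never regains 300 mg gets no Maintenance period at all. The day after the first 300 mg dose does not exist, and the fallback is only for subjects who did not enter Up-Dosing.

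**2. Switchers, Pathway 1 row.** Maintenance is all 1096 days. Used alone, it counts the 43 to 71 days of repeat up-dosing as maintenance. Used together with the Pathway 2 Up-Dosing row, those same days fall in both periods.

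**3. Direct entry to Extended Maintenance.** There is no Initial Maintenance Visit. The non-repeat Up-Dosing rule and the Maintenance fallback both need that date, so 0 of 1096 days are assigned to a component period.

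**4. Direct entry to Initial Maintenance.** The first visit is at week w = 7, 8 or 9 (Week 8 ± 1), and the subject is on 300 mg from Day 1.

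| Reading | Effect |
|---|---|
| Non-repeat rule opens Up-Dosing; a baseline in-clinic 300 mg dose closes it | 1 day labelled Up-Dosing |
| Non-repeat rule opens Up-Dosing; first in-clinic dose is at week w | 7w + 1 = 50, 57 or 64 days labelled Up-Dosing |
| Treated as never entering Up-Dosing | 7w = 49, 56 or 63 days in no component period |

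Protocol Section 7.2.1 schedules a baseline in-clinic dose for subjects who continued AR101 in the parent study, unless the visit falls on a parent-study dosing day.

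**The case against.** The strongest reply is that nothing disappears. Table 4's Overall row starts at first ARC008 dose, SAP Section 7.2 puts derived period flags in the listings, and Section 9.1 commits to listing the TEAEs of switchers. The nondaily subgroup in Section 6.3 is based on the initial ARC008 regimen, so switchers stay in it. This stands, with one reservation: Section 9.1 describes Overall as the three component periods together, which does not match the Overall row of Table 4.

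A reader might infer that the plan makes maintenance look safer than it is. The documents do not support that as a general statement. Under the Pathway 2 rows, Maintenance reactions are understated. Under the Pathway 1 row, no pre-switch event is dropped and up-dosing reactions are added to Maintenance, which works against the product. Nor is every switch driven by reactions: Protocol Section 3.1.1 also lists nonadherence and medically necessary interruptions, and subjects with reactions may be discontinued instead of switched.

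A reader might also take period columns that do not add up to Overall as proof of the gap. They are not proof. Subjects are counted once within each period, and TEAEs run to 30 days after last dose while Maintenance ends at last dose.

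For direct Extended Maintenance entrants, SAP Sections 7.1.1 to 7.1.3 do define a start of Extended Maintenance as the first visit so labelled. That definition serves the visit windows and Table 4 does not use it. The first such visit is Month 3 (Protocol Section 7.2.4), so borrowing it would still leave the earlier doses unassigned.

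Finally, SAP Appendix A and the issue-tracking documents named in Section 7.7 are not in the text available here and might hold a rule. Table 4 itself names no exception.

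**Conclusion.** Table 4 is wrong as written for two groups and unreliable for a third. Switchers' time is misassigned whichever rows are used: the whole pre-switch interval is in no component period, or 43 to 71 days of repeat up-dosing (longer if steps are delayed) are absorbed into or overlap Maintenance. Direct Extended Maintenance entrants have no defined Maintenance start. Direct Initial Maintenance entrants have 1 day mislabelled where a baseline in-clinic 300 mg dose closes the period; otherwise about 7 to 9 weeks are mislabelled or unassigned.

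The fault is confined to the component-period columns. The direction of the error depends on a choice that the SAP does not state. The numbers of switchers and direct entrants are not given, so the number of misplaced reactions cannot be computed, and the documents do not show that it is large. The day counts rest on the assumed treatment length and switch times and on an undelayed 2-week schedule. The point should be corrected because it affects tables for the primary objective and the repair is small.

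**What to change.** Rewrite the Pathway 2 rows of Table 4 as dated segments.

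- **Switchers:** first ARC008 dose to the day before repeat up-dosing is Initial and Extended Maintenance; repeat up-dosing, through the existing Table 4 end rule, is Up-Dosing; the remainder is Maintenance again.
- **Pathway 2 subjects with no up-dosing in ARC008:** Maintenance starts at first ARC008 dose, and there is no Up-Dosing period.

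Apply the corrected flags in SAP Sections 9.1, 9.2.1, 9.2.3, 9.11 and 9.12.

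The cost is reprogramming the period flags and rerunning the period tables. No new data are needed, since Table 4 already relies on the repeat up-dosing and dosing dates. SAP Section 1.1 places Version 2 after database lock and restricts its changes to Appendix A, and Section 6.1 expects analysis amendments before lock. This would therefore be a post-lock change, to be documented as such in the study report.

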Subjects in Treatment Pathway 3, having just completed the Initial Escalation Period, will receive AR101 starting at a dose of 3 mg QD and escalate every 2 weeks to a maximum of 300 mg QD, according to the Up-Dosing Schedule (Table 5). The Up-Dosing Period can last from 22 to 52 weeks.

Those subjects who reach the target dose of 300 mg QD of AR101 will take this dose for 2 additional weeks as part of the Up-Dosing Period. Subjects who do not tolerate the 300 mg QD dose of AR101 for 2 weeks within 52 weeks (ie, must reach 300 mg dose within 50 weeks) after starting the Up-Dosing Period will discontinue dosing and complete the End of Treatment visit. Once a subject tolerates the 300 mg dose for 2 weeks in the Up-Dosing Period, the subject will then enter the Initial Maintenance Period and receive the 300 mg dose

for 24 weeks. To escalate to the next dose, a subject must be tolerating the current dose (Section 6.8.2). Some subjects may require de-escalation, and once the lower dose is tolerated they may again attempt increasing the dose.

Table 5: Up-Dosing Schedule (Treatment Pathway 3)

Dose Number	Investigational Product Dose, mg ^a	Interval (Weeks)	Percent Increase From Previous Dose
1	3	2	_
2	6	2	100
3	12	2	100
4	20	2	67
5	40	2	100
6	80	2	100
7	120	2	50
8	160	2	33
9	200	2	25
10	240	2	20
11	300	2	25

^a All mg doses shown refer to milligrams of peanut protein.

3.2.3.3 Treatment Pathway 5

After completing the Initial Escalation Period, subjects in Treatment Pathway 5 will receive AR101 starting at the 1 mg/day dose and dose escalation will occur every 2 weeks until the maximum daily dose of 300 mg is reached (Table 6). Subjects who tolerate the 300 mg/day dose for 2 weeks within 40 weeks after start of up-dosing will begin the Initial Maintenance Period. Subjects who do not tolerate the 300 mg/day dose for 2 weeks within 40 weeks after start of up-dosing will discontinue dosing and complete the End of Treatment visit.

Investigational Product Percent Increase From Dose Number Interval (Weeks) Dose, mga **Previous Dose** Not applicable

Table 6: Up-Dosing Schedule (Treatment Pathway 5)

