3.2.4 Initial Maintenance Period (Pathways 2, 3, and 5)

Subjects in Treatment Pathways 2, 3, and 5 who reach the target dose of 300 mg daily of AR101 and tolerate the dose for 2 additional weeks will return for an in-clinic visit to mark the End of Up-Dosing in this study. The following day, subjects will enter the Initial Maintenance Period and continue dosing with AR101 at 300 mg QD. Dosing on study visit days will take place in the clinic under direct observation.

Subjects in Treatment Pathway 2 who completed the Up-Dosing/Repeat Up-Dosing Period or tolerated AR101 300 mg QD for 2 weeks in ARC004 will enter the Initial Maintenance Period after the ARC008 Screening/Baseline visit. Subjects who did not complete their AR101 maintenance regimen in an eligible parent study (except study ARC005) will have a Screening/Baseline visit and begin the Initial Maintenance Period in ARC008.

Subjects in Treatment Pathways 2 and 3 will return for in-clinic visits at approximately Weeks 8 and 16 of the Initial Maintenance Period before returning at Week 24 to complete this Period and enter Extended Maintenance (Figure 2).

Subjects in Treatment Pathway 5 will continue initial maintenance (with clinic visits every 4 weeks) for an overall total of approximately 12 months of treatment (including initial dose escalation, up-dosing, and maintenance treatment) (Figure 3). The duration of initial maintenance treatment may vary from a minimum of 12 weeks to a maximum of 24 weeks depending on the duration of up-dosing (24-40 weeks). Subjects in Treatment Pathway 5 will have an OLFC at the end of initial maintenance (ie, after an overall total of approximately 12 months of treatment).

Up-dosing begins with the first 1 mg/day dose of study product at home.

[figure not shown]
^a Milligrams of peanut protein.

The duration of maintenance treatment may be affected by a pandemic, epidemic, or other emergency not related to the study as described in Appendix 12.

Figure 2: Initial Maintenance Period Visits (Treatment Pathways 2 and 3)

Figure 3: Initial Maintenance Period Visits (Treatment Pathway 5)

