2.4.2.3. Up-Dosing Period (Treatment Pathways 2, 3, and 5)

The Up-Dosing Period is designed to allow stepwise increases in AR101 dose over 2-week intervals to build up tolerance to the allergen while minimizing AEs. The first dose at each new dose level will be administered in the clinic. Subsequent doses will be dispensed to the subject or parent/caregiver and administered at home.

To escalate to the next dose, a subject must be tolerating the current dose. Some subjects may require de-escalation, and once the lower dose is tolerated they may again attempt increasing the dose.

Treatment Pathway 2

Subjects who did not complete their AR101 up-dosing regimen in an eligible parent study will have a Screening/Baseline visit and continue up-dosing in ARC008, proceeding through the applicable study periods until the End of Treatment visit.

Subjects who enter ARC008 soon after completing the ARC004 Early Discontinuation visit will have a Screening/Baseline visit in ARC008 and then enter a Repeat Up-Dosing Period, starting with a daily dose of AR101 at 80, 120, or 160 mg/day at the discretion of the investigator. The dose will be increased every 2 weeks until the maximum daily dose

of 300 mg is reached. Subjects who tolerate the 300 mg/day dose for 2 weeks will receive 300 mg QD for 24 weeks in the Initial Maintenance Period. ARC004 subjects who tolerated the non-daily regimen in ARC004 but who subsequently do not tolerate the non-daily regimen after entering ARC008 Treatment Pathway 1 may switch to Treatment Pathway 2 and start the Repeat Up-Dosing Period at investigator discretion.

Treatment Pathway 3

Subjects in Treatment Pathway 3 will receive AR101 starting at a dose of 3 mg QD and escalate every 2 weeks to a maximum of 300 mg QD, according to the Up-Dosing Schedule. Those subjects who reach the target dose of 300 mg QD of AR101 will take this dose for 2 additional weeks as part of the Up-Dosing Period. Subjects who do not tolerate the 300 mg QD dose of AR101 for 2 weeks within 52 weeks (ie, must reach 300 mg dose by 50 weeks) after starting the Up-Dosing Period will discontinue dosing and complete the End of Treatment visit. Once a subject tolerates the 300 mg dose for 2 weeks in the Up-Dosing Period, the subject will then enter the Initial Maintenance Period and receive the 300 mg dose for 24 weeks.

Treatment Pathway 5

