2.4.2.4. Initial Maintenance Period (Pathways 2, 3, and 5)

Subjects in Treatment Pathways 2, 3, and 5 who reach the target dose of 300 mg daily of AR101 and tolerate the dose for 2 additional weeks will return for an in-clinic visit to mark the End of Up-Dosing in this study. The following day, subjects will enter the Initial Maintenance Period and continue dosing with AR101 at 300 mg QD. Dosing on study visit days will take place in the clinic under direct observation.

Subjects in Treatment Pathway 2 who completed the Up-Dosing/Repeat Up-Dosing Period or who tolerated AR101 300 mg QD for 2 weeks in ARC004 will enter the Initial Maintenance Period after the ARC008 Screening/Baseline visit. Subjects who did not complete their AR101 maintenance regimen in an eligible parent study (except study ARC005) will have a Screening/Baseline visit and begin the Initial Maintenance Period in ARC008.

Subjects in Treatment Pathways 2 and 3 will return for in-clinic visits at approximately Weeks 8 and 16 of the Initial Maintenance Period before returning at Week 24 to complete this Period and enter Extended Maintenance.

Subjects in Treatment Pathway 5 will continue initial maintenance (with clinic visits every 4 weeks) for an overall total of approximately 12 months of treatment (including initial dose escalation, up-dosing, and maintenance treatment). The duration of initial maintenance treatment may vary from a minimum of 12 weeks to a maximum of 24 weeks depending on the duration of up-dosing (24-40 weeks). Subjects in Treatment Pathway 5 will have an open-label food challenge (OLFC) at the end of initial maintenance (ie, after an overall total of approximately 12 months of treatment).

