9.11. STUDY TREATMENT EXPOSURE

The calculation of exposure will be based on in clinic dosing data and at home dosing as captured on the Study Product Exposure CRF page.

First and last dose dates for each study period are identified as described in Section 7.5.

The total amount of study product consumed will be calculated as the sum of in-clinic doses plus the estimated number of doses taken at home. At-home doses will be estimated by combining the doses across each dosing interval entered on the Study Product Exposure CRF page and taking into account the dosing frequency and any missed and partial doses as captured on the Subject Dosing Diary CRF.

The following calculations of study drug exposure will be made and summarized:

• Duration of Exposure (in days and in years): calculated as the date of last dose of study drug minus the date of the first dose of AR101 plus one during the study

> period, except for the Initial Escalation period, where the duration of exposure will only be 1 or 2 days depending on whether drug was taken on Initial Escalation Day 1 and Initial Escalation Day 2. Duration of exposure will be summarized using descriptive statistics for continuous data as well as categorically by 28-day increments for the first year and by year for the overall treatment periods: \leq 28 days, 29 to 56 days, 57 to 84 days, ..., 1 to < 2 years, 2 to < 3 years, 3 to < 4 years, 4 to < 5 years, and \geq 5 years.

- Total dose consumed (mg): calculated as the cumulative sum of all doses taken during the study period.
- Average dose per day (mg): calculated as the total dose consumed divided by the number of days during the study period.
- Maximum dose achieved (mg/day): summarized using descriptive statistics for continuous data as well as categorically using all possible dose levels: 0.5, 1, 1.5, 3, 6, 12, 20, 40, 80, 120, 160, 200, 240, or 300 mg/day.
- Number of unsuccessful dose increases: calculated as the number of single doses given at the study site at a higher dose level followed by an immediate return to the previous dose level or a lower dose level.
- Number of dose reductions: calculated as the number of any decrease in dose level given at the study site that does not qualify as an unsuccessful dose increase.

Study treatment exposure parameters will be summarized by the following study periods:

- Initial Escalation
- Up-Dosing
- Initial and Extended Maintenance

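### SAP Table 4 closes Up-Dosing on the day of the first in-clinic 300 mg dose, so the rest of the top dose step, and any step-down after a failed first 300 mg dose, is tabulated as Maintenance

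*SAP*

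**What the plan says.** SAP Table 4 creates the study period flags. For Pathways 2, 3 and 5 the Up-Dosing period ends at 23:59:59 on the "Date of first in-clinic dose of 300 mg during the Up-Dosing period". The only exception is for subjects who never reach 300 mg. Initial and Extended Maintenance then begins on "The day following the date of first in- clinic dose of 300 mg during the Up- Dosing period".

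The design text draws the line elsewhere. Protocol 3.2.3.2 says of Pathway 3 subjects who reach 300 mg that they "will take this dose for 2 additional weeks as part of the Up-Dosing Period", and SAP 2.4.2.3 agrees: "Once a subject tolerates the 300 mg dose for 2 weeks in the Up-Dosing Period, the subject will then enter the Initial Maintenance Period". For Pathways 2, 3 and 5 together, Protocol 3.2.4 says that subjects who reach 300 mg and "tolerate the dose for 2 additional weeks will return for an in-clinic visit to mark the End of Up-Dosing in this study". SAP 2.4.2.4 repeats this and continues: "The following day, subjects will enter the Initial Maintenance Period and continue dosing with AR101 at 300 mg QD".

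SAP Section 13, which lists changes from the protocol's planned analysis, does not mention the period boundary.

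**The concern.** Treatment-emergent adverse events (SAP 9.1), anaphylaxis (9.2.1), food allergy episodes (9.2.3), exposure (9.11) and rescue medication (9.12) are all tabulated by study period. Under Table 4 as written, the Up-Dosing columns keep only the first day at 300 mg. The Maintenance columns receive the rest of that dose step.

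The missing tolerance condition is the more awkward part. A subject who takes one 300 mg dose in clinic, reacts and steps down has reached 300 mg, so the exception does not apply. That subject is flagged Maintenance while on a reduced dose and while re-attempting 300 mg. This holds even for a Pathway 3 subject who never tolerates 300 mg for two weeks and so, under Protocol 3.2.3.2, never enters Maintenance. If the flags also drive SAP 8.1, that subject is counted as having entered it.

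Table 4 also misplaces Pathway 2 subjects who skip up-dosing in ARC008. What is at stake is how the by-period safety and exposure tables read in a study whose primary objective is safety and tolerability.

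**Working it through.** **Inputs.** Pathway 3: 11 dose levels of 2 weeks (Protocol Table 5), 22 to 52 weeks, 300 mg reached within 50 weeks (3.2.3.2). Repeat Up-Dosing: levels 80, 120, 160, 200, 240 and 300 mg, starting at 80, 120 or 160 mg (Protocol Table 4). Pathway 5: 24 to 40 weeks (3.2.4); its dose table is not readable in the text available, so 24/2 = 12 levels is an assumption. Day 1 is the first Up-Dosing day, with no delays.

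**1. Reproduce the plan's own figures (Pathway 3).** 11 × 2 = 22 weeks, the stated minimum, only if the 300 mg step counts as Up-Dosing. 52 − 2 = 50 weeks, the stated limit for reaching 300 mg. From 6 to 300 mg there are 10 new-level visits; with the end visit that makes 11, as Protocol 7.3.3 states. The first in-clinic 300 mg dose is therefore not the End of Up-Dosing visit dose; the protocol lists the two visits separately.

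**2. Days moved.** With L levels, Table 4 closes on day 14(L − 1) + 1 and the end visit falls on day 14L + 1. The difference is always 14 days.

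| Pathway | L | Table 4 end | End visit | Share moved |
|---|---|---|---|---|
| 3 | 11 | 141 | 155 | 14/155 = 9.0% |
| 5 (assumed) | 12 | 155 | 169 | 14/169 = 8.3% |
| 2, from 80 mg | 6 | 71 | 85 | 14/85 = 16.5% |
| 2, from 120 mg | 5 | 57 | 71 | 14/71 = 19.7% |
| 2, from 160 mg | 4 | 43 | 57 | 14/57 = 24.6% |

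**3. Up-Dosing exposure.** SAP 9.11 defines "Average dose per day (mg): calculated as the total dose consumed divided by the number of days during the study period".

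- Pathway 3: the ten levels below 300 mg sum to 881 mg.
  - To day 141: 14 × 881 + 300 = 12,634 mg; 12,634/141 = 89.6 mg/day.
  - To day 155: 12,634 + 14 × 300 = 16,834 mg; 16,834/155 = 108.6 mg/day.
  - Change: −24.9% in total dose, −17.5% in average dose.
- Repeat Up-Dosing from 80 mg: 11,500 against 15,700 mg (−26.8%); 162.0 against 184.7 mg/day (−12.3%).
- Repeat Up-Dosing from 160 mg: 8,700 against 12,900 mg (−32.6%); 202.3 against 226.3 mg/day (−10.6%).

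**4. Failed first 300 mg dose.** Protocol 6.9.3 governs a first dose at a new level that is not tolerated. Its shortest path is one level down for 2 weeks. If 300 mg is then tolerated for 2 weeks, about 14 + 14 = 28 days move, or 28/(155 + 14) = 16.6% of Pathway 3 Up-Dosing. Longer holds in that section move more. The first failed attempt is still dated in Up-Dosing; failed re-attempts at 300 mg are dated in Maintenance.

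**5. Share of Maintenance.** Taking 2 days of Initial Escalation and the treatment totals in Protocol 3.2.6:

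- Pathway 3 over 5 years: 1826 − 2 − 141 = 1683 days; 14/1683 = 0.8%.
- Pathway 5 over 3 years: 1096 − 2 − 155 = 939 days; 14/939 = 1.5%.

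The share is larger for anyone who stopped sooner, for example 14/365 = 3.8% with one year of Maintenance.

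**6. Pathway 2 direct entrants.** Without Repeat Up-Dosing, Table 4 starts Up-Dosing at the first ARC008 dose if that precedes the first Initial Maintenance visit. That visit is Week 8 (Protocol 7.2.3), so a subject entering directly at Initial Maintenance meets the rule without up-dosing. The wrong flag lasts 1 day if 300 mg is given in clinic at Screening/Baseline. Otherwise it can last to the Week 8 visit, 56 ± 7 = 49 to 63 days. A subject entering directly at Extended Maintenance has no Initial Maintenance visit, so Table 4 supplies no Maintenance start date.

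**The case against.** The best defence is that Section 7.4 is the operative definition and Section 2.4 only summarises the design. SAP 1.1 says Version 1 was approved before database lock and Version 2 changes only Appendix A, so the Table 4 rule was prespecified. A recorded in-clinic 300 mg dose is also a firmer anchor than a visit label that may be missing after remote visits, and home doses are estimated (SAP 9.11). The study is descriptive and no endpoint is defined by period, so a footnote might be enough.

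Much of this stands, and it limits the size of the point. It does not make a failed 300 mg dose the start of Maintenance, and it does not explain why Section 13 is silent.

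A reader might infer more than the documents support:

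- *That overall safety results are wrong.* ARC008 overall exposure does not change. Overall subject frequencies do not change either, provided Overall covers the whole treatment-emergent window.
- *That the −24.9% carries over to event rates.* It is an Up-Dosing exposure figure on an ideal schedule; the effect on event rates cannot be computed.
- *That Pathway 1-to-2 switchers lose their pre-switch time.* Table 4 does not say that only the Pathway 2 rows apply to them. The Pathway 1 row, used first, would cover it.
- *That events on days 1 to 30 after last dose drop out.* SAP 9.1, 9.2.1 and 9.2.3 describe Overall as three on-treatment periods, but Table 4's Overall runs to Study Exit and would include them.

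**Conclusion.** The point holds. Table 4's boundary contradicts the protocol and the SAP's design text. The contradiction is outright for Pathway 3; for Pathways 2 and 5 it follows from the placing of the End of Up-Dosing visit. At least 14 days per subject who completes up-dosing move to Maintenance, and more after a failed first 300 mg dose. The proportional effect is noticeable in Up-Dosing and small in Maintenance (about 0.8% to 1.5% at the planned durations). The handling of Pathway 2 direct entrants is a separate gap in the same table.

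The figures assume the minimum schedule, full dosing and, for Pathway 5, 12 levels. The documents give no counts of failed attempts, direct entrants or affected events. The consequence is confined to by-period safety, rescue-medication and exposure tables. It should be corrected, but it does not threaten the study's overall safety description.

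**What to change.** First check whether the tracking documents named in SAP 7.7 already deal with this. If they do not:

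- For subjects who up-dose in ARC008, end Up-Dosing on the End of Up-Dosing visit date and start Maintenance the next day.
- If that visit is missing, use the date on which 2 consecutive weeks at 300 mg were completed according to the exposure CRF.
- For subjects who never complete 2 weeks at 300 mg, end Up-Dosing at last dose.
- For Pathway 2 subjects entering directly at Initial or Extended Maintenance, set no Up-Dosing period and start Maintenance at the first ARC008 dose.
- Rerun the by-period tables as a documented post-lock correction in the CSR, stating both the prespecified Table 4 rule and the change.

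Two items need only a clarifying sentence: which Table 4 rows cover a switcher's time before Repeat Up-Dosing, and which column carries treatment-emergent events on days 1 to 30 after last dose.

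The cost is reprogrammed flags, rerun tables and a visible post-lock change. No new data collection is needed, but the fallback rests partly on estimated home dosing.
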